### **3.0 Study Endpoints/Events/Outcomes**

Primary Endpoint/Event/Outcome:

Our primary endpoint will be reduction in pain intensity assessed by the International Spinal Cord Injury Pain Data Set.

Secondary Endpoint(s)/Event(s)/Outcome(s):

Secondary outcomes include brain resting state and task based activity and functional connectivity and various psychosocial factors related to participants' experiences with SCI, such as change in mood, satisfaction with life, community integration, sleep, self-efficacy, pain catastrophizing, perceived disability, and spasm frequency.

### **4.0 Study Intervention(s)/Investigational Agent(s)**

Description:

Intervention: brivaracetam or placebo administration. [name] (Co-I/study physician) currently holds an Investigational New Drug (IND) application for brivaracetam to treat severe neuropathic pain in individuals with SCI (IND # 150388). With regulatory support provided by UMN CTSI, we will submit this protocol to the FDA for review under the existing IND upon notification of funding. RxArtisans Pharmacy (Wayzata, MN) will FedEx the drug to the participant directly (study staff will send an email notification to the participant that the drug has been sent by overnight

mail) or to the designated contact at the enrolling site for distribution. To minimize wasting of drug, RxArtisans will dispense and ship prescriptions concurrent with the ramp-up schedule (weekly, biweekly, or as requested by study doctor). Participants will be asked to verify by phone or email receipt of study drug and initiation of the treatment course.

Drug dosage will be individually titrated for each participant with a goal of 100mg BID according to the following dose escalation protocol that we use clinically: 50mg BID for 1 week followed by 100mg BID for 28 days as tolerated. Participants will be allowed to reduce the dose of brivaracetam if they experience unacceptable side effects defined as increased somnolence according to routine clinical practice with other drugs in this class used for pain. Participants will be given an additional week to ramp up to 100mg BID, as needed. The 28-day treatment period might also be extended in the case of illness or other unanticipated event that impacts the ability to take the medication consistently. This will be determined on a case-by-case basis by the study team. The treatment course will be recorded and considered in analysis. A dose of 50mg BID or higher must be maintained to complete the trial. The study drug will be paid for by the study.

Drug discontinuation at study completion will be done according to the following protocol we use clinically that will be initiated for 2 weeks following end of study testing (Visit 3): reduction to 50mg BID for 1 week followed by 50mg daily for 1 week. For those at the highest study tolerated dose of 50mg BID, the dose will be reduced to 50mg daily for 1 week and then stopped. At the end of the two-week ramp down, participants will mail any remaining pills and the empty pill bottle along with the medication diary using self-addressed and prepaid packaging. University of Minnesota Investigational Drug Services (IDS) will register the study, while Rx Artisans will be dispensing the drug.

If a participant is admitted to the hospital for any reason during the course of the study, the participant or physician will notify the study coordinator or study PI using the phone number contained on the consent form or printed on the medication bottle. The PI/study coordinator will immediately notify the blinded study physician ([name]) who will contact the unblinded medical monitor ([name]). The two will decide whether unblinding is warranted. If warranted, the medical monitor will access the unblinding key that is stored in a password-protected file that only he and the pharmacy can access. The medical monitor will follow up with the treating physician and provide

the drug information (i.e., placebo or study drug) within 30 minutes of notification. The process for emergent unblinding will be available 24 hours a day, 7 days a week.

At the beginning of the study, all participants are directed that if in this situation, they are to bring study medication to the hospital and inform the physician overseeing the hospital stay that they are taking a research-related study drug. Further, the medical professional should assume that they are on the study drug. He/she may reach out for more information about the study drug.

**Drug/Device Handling:**

Brivaracetam or placebo will be compounded and dispensed by RxArtisans Inc. The active drug will be placed without modification into the appropriate gelatin capsule. Each strength of active and placebo will have an identical capsule color and inactive ingredients (microcrystalline cellulose and silica gel). Study investigators will send a prescription to the pharmacy, and the pharmacy will dispense the appropriate study medicine. The study medicine will then be provided to research volunteers at UMN or via FedEx/courier delivery in the United States. Study staff will confirm with each participant by phone (or participant-preferred communication including email, text, etc.) that the drug was received.

Biosafety: N/A

Stem Cells: N/A

Fetal Tissue: N/A

## **5.0 Procedures Involved**

**Study Design:**

This is a randomized, double-blind, placebo-controlled clinical trial in 40 adults at least 18 years of age with SCI. Participants who meet the eligibility criteria (described in Section 8.1) will be randomly assigned with a 1:1 ratio to active drug (escalating brivaracetam dose to 100 mg twice daily for four weeks) or placebo using a randomization schedule developed by our biostatistician. This is a simple computer generated 1:1 scheme that randomly assigns participants to arm C or arm D. Study participants, research coordinators, and study personnel involved in outcomes assessments and analyses will all be masked to allocation. The drug will be provided by RxArtisans pharmacy in Wayzata, MN. The active and placebo capsules will have identical appearance and consistency. Treatment assignment will be known only to the investigational drug pharmacy (RxArtisans). We will register this trial at [www.clinicaltrials.gov](http://www.clinicaltrials.gov).

Study Procedures:

Overview of study procedures/study interventions. This study involves research activities that occur in-person, over the phone, and via online REDCap surveys. Participants will also have the option to participate entirely remotely. In this circumstance, there will be no MRI scan nor blood draw for banking; instead, all required safety labs will be completed with the participant's primary care physician and insurance will be charged and the participant will be responsible for any associated copays or costs. All research activities are summarized in Table 1 below and described in detail in the subsequent text.

Screening: A phone screen will be administered to confirm basic eligibility criteria listed in Section 8.1 such as age, pain level, medication use, and other medical conditions. Study staff will also screen for MRI contraindications at that time with the Center for Magnetic Resonance Research (CMRR) pre-screening questionnaire (i.e., implanted medical devices or retained metal fragments). Eligible individuals will be required to receive medical clearance from their primary care provider within one month of (prior to) Visit 1, including physical exam, health history, and lab work to confirm normal renal function, absence of liver cirrhosis, and absence of pregnancy. While we will target obtaining lab work within 1 month of baseline, labs up to 6-weeks prior to baseline will be accepted to reduce participant burden. Their insurance will be charged, and they will be responsible for any associated copays or costs.

For participants who recently had comprehensive metabolic panel done, medical record review of lab results can replace new screening labs if the blood labs were completed within one month of (prior to) the scheduled baseline appointment. If the participant is seeing a provider in-system, the study coordinator will pull labs from the medical record. If the participant is not seeing a provider in-system, the study coordinator will instruct the participant's physician to fax the lab report to the study coordinator. The instructions for faxing will be on the screening eligibility sheet the participant brings to their doctor's appointment and available to be emailed for the participant upon request.

Visit 1: This visit includes informed consent, randomization, a focused physical exam, and a mental health and health history screen. CDE-recommended questionnaires relating to pain, mood, active suicidality, satisfaction with life, kinesiophobia, sleep quality, and community integration will also be administered.

Visit 2: This visit may be combined with Visit 1, if the participant prefers. Visit 2 includes an optional blood draw for batch analysis and an optional MRI scan; the optional MRI and optional blood draw are paid for by the study. Visits 1 and 2 can take place either at the study site or virtually, depending on participant preference. Those who choose to participate in the study virtually will not take part in the MRI or blood draw. For participants with contraindications to MRI, the MRI will not be completed.

Once randomized, the 7-week supply of study drug will be dispensed and mailed directly to participants to begin 7 weeks of active treatment or placebo, as described in Section 4.0. All participants will receive a medication diary to track study drug compliance and to record medication use.

Weekly phone check-in: Masked data collectors will perform weekly check-in calls to assess for medication-related adverse events (AEs). The data collector will also administer the Patient Health Questionnaire 9-item (PHQ-9) to assess for changes in mood and suicidality. A suicide protocol will be initiated if a participant endorses suicidality (see below). Participants will also report on their level of pain (rate highest, lowest, and average pain (0-10) that day). Reported AEs identified in these calls will be documented and immediately shared with the PI for review.

Suicide Protocol: Endorsement of active suicidality on PHQ-9 will trigger the suicide protocol. Study staff will call 911 in the event of a psychological emergency noted during a phone call (credible report of intent to harm oneself). Study staff will first ask to speak to another adult in the household. If none is present or comes to call, study staff will call 911 and remain on the line until first responders arrive. In the event of a non-emergent psychological situation (psychological distress in the absence of intent for self-harm), study staff will refer the participant to their PCP or the National Suicide Hotline ([name]). In either case, study staff will notify the PI immediately.

Visit 3: End of intervention assessments will be repeated 5 weeks after Visit 2. This includes a focused physical exam, a mental health and health history screen, optional blood draw, optional MRI, and questionnaires relating to pain, mood, active suicidality, satisfaction with life, kinesiophobia, sleep quality, and community integration. Additionally, limited safety labs will be repeated (from pre-Visit 1) to confirm normal renal function, absence of liver cirrhosis, and absence of pregnancy in individuals of childbearing potential. The fasting blood draw and analysis

will occur either at the enrolling site or with the participant's primary care provider, based on participant preference. Blood will be analyzed for blood urea nitrogen (BUN), creatinine, alanine transaminase (ALT), aspartate transaminase (AST), total bilirubin, albumin, GFR, calcium, corrected calcium, and human chorionic gonadotropin (hCG); urine hCG test will also be accepted. International normalized ratio (INR) will be collected at the discretion of the participant's primary care provider if the participant is on anticoagulation or has abnormal liver function tests. People who are menopausal and have not had a menstrual period for at least 12 months, or people who have had a hysterectomy will not be required to take pregnancy tests. Results of the pregnancy test will be sent only to study staff. At the end of Visit 3, study staff will provide instruction for the first week of the two-week dose reduction period. Data collectors will continue weekly check-ins throughout the ramp down period and up until Visit 4. Data collectors will also remind the participant to return the remaining pills and pill bottle along with the medication diary using the pre-paid envelope provided by study staff.

Visit 4: Visit 4 occurs 1 month following the end of study drug. Data collectors will assess for AEs, changes in mood and suicidality via the PHQ-9, medications, and pain levels; surveys related to mood, satisfaction with life, community integration, fear of movement related to pain, and sleep will also be administered at this time.

Our primary endpoint is reduction in pain intensity assessed by the International Spinal Cord Injury Pain Data Set. Secondary outcomes include reduction in opioid use, change in mood, satisfaction with life, community integration, brain resting-state functional connectivity, and task-based brain activation and connectivity, sleep, neuropathic pain, self-efficacy, pain catastrophizing, perceived disability, spasm frequency, and intervention expectations. The specific study measures are listed below:

*International Spinal Cord Injury Pain Data Set.* This tool assesses average pain intensity in the last week using a 0-10 numerical rating scale. The 0-10 numerical rating scale has been recommended by the IMMPACT consensus group for use in pain clinical trials [Dworkin et al., 2005] and by the 2006 NIDRR SCI Pain outcome measures consensus group. [Bryce et al., 2007] This scale is recommended to standardize pain outcomes across studies. The International Spinal Cord Injury Pain Data Set also assesses dimensions of pain (i.e., intensity of pain, time of day, location, occurrence, etc.), and pain interference with mood, activity, and sleep.

*Modified Brief Pain Inventory (BPI).* The BPI is a short self-assessment questionnaire that provides information on various dimensions of pain including how pain developed, the types of pain a patient experiences, and time of day pain is experienced, as well as current ways of alleviating pain [Cleeland and Ryan, 1994]. The BPI also consists of the numeric pain rating scale, a simple 10-point scale (0 = “no pain”, 10 = “pain as bad as you can imagine”) measuring a patient’s worst pain and least pain, on average in the last 24h and at present time. The Brief Pain Inventory provides information on the intensity of pain (the sensory dimension) as well as the degree to which pain interferes with function (the reactive dimension). According to several previous studies on pain in spinal cord injury, the BPI is an effective measure [Bryce et al., 2007].

*DN4 Assessment Tool.* This is a 4-item assessment that characterizes neuropathic pain.

*Assessment of Mood with the Patient Health Questionnaire (PHQ-9).* This is a 9-item scale that assesses patient quality of life through mental state. It identifies active suicidality [Kroenke et al., 2001]. It assists physicians in both diagnosing depression and determining a treatment route. It incorporates DSM-IV depression classifications and determines severity of depression [Bombardier et al., 2004; Graves and Bombardier, 2008; Kalpakjian et al., 2009; Krause et al., 2010].

*Satisfaction with Life Scale (SWLS).* This is a 5-item scale that assesses patient happiness with current quality of life [Diener et al., 1985]. It consists of a 1-7 Likert scale.

*Craig Handicap Assessment and Reporting Technique – Short Form (CHART-SF).* This assessment is commonly used to provide an objective measure as to the degree by which a person with SCI remains with impairment or disability [Whiteneck et al., 1992]. It measures several domains including: the type and level of daily assistance needed on both a physical and cognitive level (i.e., personal care, hygiene, decision making, communicating with others); level of physical activity (ranging from travel to daily mobility); transportation needs how time is spent (i.e., employment, housekeeping, cooking, leisure activities); social interactions (including relatives, co-workers, and friends); and available financial resources.

*Posttraumatic Stress Symptoms (PTSS).* The PTSD Checklist for DSM-5 (PCL-5) is a 20-item self-report measure assessing symptoms of PTSD.

Participants rate how bothered they have been by each of the 20 items in the past month on a 5-point scale ranging from 0 (not at all) to 4 (extremely). Scores range from 0-80, with higher scores indicating greater severity of PTSD symptoms. The PCL-5 is psychometrically sound in civilians and Veterans.

*Childhood Trauma.* The Adverse Childhood Experiences Questionnaire (ACE-Q) is a 10-item measure to quantify instances of adverse or traumatic experiences that a person has had before the age of 18. The ACE-Q will be asked at baseline and screens for exposure to childhood psychological, physical, and sexual abuse as well as household dysfunction including domestic violence, substance use, and incarceration.

*Pittsburgh Sleep Quality Index.* This is a 9-item scale that assesses sleep quality.

*Tampa Scale for Kinesiophobia.* This is a 17-item scale that assesses fear of movement.

*Moorong Self-Efficacy Scale (MSES).* This is a 16-item scale that assesses self-efficacy in performing functional activities of daily living individuals with SCI.

*Pain Catastrophizing Scale (PCS).* This 13-item self-report measure is designed to assess catastrophic thinking related to pain among adults with or without chronic pain.

*Perceived Disability Index (PDI).* This is a brief, self-report instrument developed to assess self-perception of disability.

*Penn Spasm Frequency Scale (PSFS).* This is a self-report measure that assess a patient's perception of spasticity frequency and severity following a spinal cord injury.

*Bladder and bowel function.* Nine self-report items will assess current bladder and bowel functioning.

*Intervention Expectations.* This self-report will assess what participants expect their outcomes to be during and after their participation in the study.

*Study Expectancies.* Participants respond to 24 items about how they think they will function 7 weeks from now in areas such as pain, sleep, participation, work, social activities, and sexual functioning.

*Concurrent Pain Medication Use.* Although pain medications can confound the analgesic effects of brivaracetam, we consider it to be unethical to require participants to discontinue pharmacologic treatment for pain over the course of the study as a criterion for enrollment. In addition, to increase generalizability, it is important to recruit participants using pain medications. Therefore, we will record pain medication use over the course of the trial and consider this in the analysis.

*Pain Intensity and Medication Use Diary.* We will monitor daily pain reports and patient medication throughout the course of the study using a Pain Intensity and Medication Use Diary. Participants will be asked to record daily pain ratings (highest pain 0-10, lowest pain 0-10, and average pain 0-10) and any pain medication use. This diary will be started 1 week prior to drug treatment and maintained until completion of the study.

*Assessment of Brain Function with MRI.* All scans will be performed on the same scanner for this study. We will use the Siemens 3-T Prisma multi-band scanner. Prior to each scan, participants will be asked five questions regarding their pain now and over the last week as well as alcohol, caffeine, and tobacco use over the past 12 hours.

1. Structural MRI acquisition: We will acquire a T1-weighted Magnetization-Prepared Rapid Acquisition with Gradient Echo (MPRAGE) image [Repetition Time (TR)=2.5s, Echo Time (TE)=4.5ms, 0.8mm^3 voxels], and a T2 weighted Sampling Perfection with Application optimized Contrasts using different flip angle Evolution (SPACE) image [TR=3.2s, TE=565ms, 0.8mm^3 voxels]. We use special sequences for the scans to reduce the impact of head motion.
2. Resting-state and task fMRI acquisition: The resting-state and task fMRI scans will be obtained with a T2\*-weighted multiband echo planar acquisition tipped 30 degrees relative to the Anterior Commissure - Posterior Commissure (AC-PC) plane as determined by the auto-align software. This acquisition protocol is designed to measure whole-head BOLD-contrast with optimal temporal and spatial resolution, and to reduce signal dropout [TR=0.8s; TE=37ms; Flip Angle=55°; 72 slices; multiband factor 8; 2mm isotropic resolution]. We will use the Framewise Integrated Real-time MRIMonitoring (FIRMM)

software to track head motion for each fMRI scan in real time. If visual inspection or FIRMM shows that image quality is substandard, the scan will be repeated immediately. After the MRI acquisition, a structured Quality Assurance (QA) process will occur within 72 hours to ensure that the data are of sufficient quality for subsequent analysis. Adhering to these QA procedures should result in over 95% usable data.

- i. Task 1: Mental body scan. Participants will be asked to focus with gentle, non-judgmental awareness on the sensations of the leg (that they experience having the most pain). In other words, they perform a gentle focused mental body scan and register any feelings of sensation in that limb. We alternate this task with rest periods. We chose Task 1 based on our previous study in adults with chronic low back pain showing OP1/OP4 and posterior parietal cortex activation after body awareness training during a similar task. Other brain imaging research showed that doing a mindful mental body scan significantly increases insula connectivity.
- ii. Task 2: Kinesthetic imagery of moving the limb. Participants will be asked to imagine the feeling of gently moving the painful leg (i.e., gentle non-judgmental awareness of any sensations during an imagined movement), alternated with rest. We chose this task based on tasks with mindfulness meditation showing insula and OP1/OP4 activation.
- iii. Task 3: Whole-body movement task. Participants will perform a kinesthetic imagery of a whole-body movement, in which the hands are moving away and closer to the body symmetrically with guided breathing after viewing a video demonstration of the movement. We chose task 3 based on studies that demonstrate substantial spatial overlap of areas activated during motor imagery vs. motor execution. Our prior studies showed OP1/OP4 and posterior parietal cortex activation during this task in adults with chronic low back pain. We showed stronger insula connectivity after CMR in adults with SCI/D.
- iv. Task 4: Sensory stimulation task of the pads of the big toes and thumbs with a towel. Participants will not be made aware of when stroking occurs and will be asked after the scan if they sensed any hand or foot stimulation and, if so, where exactly they felt the stimulation.
- v. Task 5: Finger tapping. The participant is instructed verbally to tap their right fingers

MEDICAL PROTOCOL (HRP-590)

PROTOCOL TITLE: Brivaracetam to Reduce Neuropathic Pain in Chronic SCI: A Randomized, Double-Blind, Placebo-Controlled Clinical Trial

VERSION DATE: v7.0 APR2024

- vi. Task 6: Toe tapping. The participant is instructed verbally to tap their right foot. The task is alternated with rest.

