**Use of radiation: N/A**

**Use of Center for Magnetic Resonance Research:**

All participants who consent to MRI testing will get a 3T structural and functional MRI scan at Visit 2 and after completion of the 7-week treatment course (Visit 3). They will use the changing room to change into scrubs according to the CMRR protocol.

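### The screening pregnancy test can be 6 weeks old at baseline, and no repeat test is scheduled before the first dose

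*Combined protocol and SAP*

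**What the plan says.** - **Screening.** Sections 5.0 and 8.0 require lab work before Visit 1 to show, among other things, that the participant is not pregnant. Section 8.0 lists hCG in the panel, makes a positive result a screen failure, and exempts participants who are menopausal or have had a hysterectomy. The target is labs within one month, but "labs up to 6-weeks prior to baseline will be accepted to reduce participant burden". Section 8.0 repeats the 6-week allowance. Neither section treats hCG differently from the other labs.
- **Visits 1 and 2.** Visit 1 is consent, randomization, examination, history and questionnaires. Visit 2 adds an optional blood draw for batch analysis and an optional MRI. Of Visit 2 the protocol says: "This visit may be combined with Visit 1, if the participant prefers". No pregnancy test is listed at either.
- **Dispensing.** Section 5.0: "Once randomized, the 7-week supply of study drug will be dispensed and mailed directly to participants". Section 4.0, Drug/Device Handling: "Study investigators will send a prescription to the pharmacy, and the pharmacy will dispense the appropriate study medicine". Neither sentence makes a pregnancy test a condition.
- **Diary.** Section 5.0 starts the pain and medication diary one week before drug treatment.
- **Next test.** "End of intervention assessments will be repeated 5 weeks after Visit 2", and that assessment (Visit 3) includes hCG. In Table 1 the pregnancy-test row is marked only at Visit 3. For the Visit 3 test, "urine hCG test will also be accepted"; Section 8.0 allows the same at screening.
- **Safeguards.** Section 8.0 requires two types of birth control with a failure rate below 1% per year when used consistently and correctly, and excludes pregnancy. Section 12.0 lists a positive test as a reason for discontinuation.

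**The concern.** A negative test shows that a participant was not detectably pregnant on the day of the sample. The eligibility rule and the safety statement in Section 8.0 concern her status when drug exposure starts. As written, several weeks can separate the two, with nothing scheduled in between that would detect a conception.

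The later safeguards work only after exposure has begun. Discontinuation for a positive test depends on a test being done, and none is scheduled before Visit 3. The weekly calls cover adverse events, the PHQ-9 and pain ratings, not pregnancy. Only a test before the first dose can prevent exposure altogether. What is at stake is fetal exposure in a rare case; the efficacy comparison is not affected.

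**Working it through.** The plan gives no figure of its own to reproduce. The check is a timeline and a simple risk calculation.

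**Inputs**
- Maximum accepted lab age at baseline: 6 weeks = 42 days (Sections 5.0 and 8.0).
- Pre-drug diary: 1 week = 7 days (Section 5.0).
- Contraceptive failure ceiling: 1% per year with consistent, correct use (Section 8.0).
- Enrolment: up to 48 participants (Section 10.0). The number of child-bearing potential is not given.

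**Age of the hCG result**
- At baseline: up to 42 days.
- At first dose, with Visits 1 and 2 combined and the diary week starting that day: 42 + 7 = 49 days, provided the drug arrives within that week.
- With separate visits it can be older, because no maximum gap between Visit 1 and Visit 2 is stated.
- If the one-month limit governed (taken as 30 days): 30 days at baseline and 30 + 7 = 37 at first dose, still with no repeat test.

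**Chance of conception in the window, per participant of child-bearing potential**

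Formula: 1 − (1 − annual rate)^(days/365).
- 42 days at 1%: 1 − 0.99^(42/365) = 0.00116, about 0.12%.
- 49 days at 1%: 1 − 0.99^(49/365) = 0.00135, about 0.13%.

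**Trial-wide ceiling**

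Suppose, as an extreme, that all 48 were of child-bearing potential and all had results of maximum age. Expected conceptions over 49 days would be 48 × 0.00135 = 0.065, about half of them (0.03) on active drug under 1:1 allocation. The true figure is lower in proportion to the share of such participants.

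**Sensitivity to contraceptive failure (assumed rates, not in the documents)**
- 5% per year over 42 days: 1 − 0.95^(42/365) = 0.59%.
- 10% per year over 42 days: 1 − 0.90^(42/365) = 1.2%.

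**The case against.** The strongest reply is that entry is already gated. Nobody should be randomized or sent drug without a negative hCG, two contraceptive methods are required, and Visit 1 includes a history and examination. The 6-week limit is an outer tolerance around a one-month target, introduced in version 5.0 with participant burden as the stated reason. Even under upper-bound inputs, the expected number of conceptions across the whole trial is well below one.

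All of that stands, and it keeps the point at low severity. It does not close the gap: the 6-week allowance is explicit, and even the one-month limit leaves no test between screening and first dose.

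Four stronger readings are tempting, and the documents do not support them:

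- **That dosing proceeds with no pregnancy check.** Section 8.0 makes a positive screening hCG a screen failure. What is missing is a repeat test.
- **That screening hCG is missing because Table 1 marks the test only at Visit 3.** Table 1 marks safety labs at Screening, and Section 8.0 puts hCG in that panel. Marking it in the pregnancy-test row would be a clerical edit, as would aligning the one-month and 6-week wording.
- **That the whole interval from screening to the Visit 3 test measures the problem.** Much of it is time on treatment, which a pre-dose test would not change.
- **That a shorter window cuts the risk in proportion to its length.** Shipping and the diary week still follow the prescription, and hCG cannot detect a very recent conception. The documents give no detection lag, so no percentage reduction is claimed here.

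**Conclusion.** The point holds as a low-severity safety gap. A negative screening hCG is required, but it may be 42 days old at baseline and about 49 days old at first dose, and no repeat test is scheduled until Visit 3.

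The chance of conception in that window is about 0.12% to 0.13% per participant of child-bearing potential. This assumes the maximum permitted lab age and failure at the full 1% ceiling. It also assumes contraception was used correctly throughout the window, whereas the criterion describes current practice. The 49-day figure further assumes that the diary week begins at a combined Visit 1/2.

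Sample size, power, type I error and the primary endpoint are unaffected.

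**What to change.** Keep the 6-week window for renal and liver labs. For participants of child-bearing potential, add one sentence requiring a negative urine or serum hCG either at Visit 1/2 or within a short set interval before the first prescription is sent to the pharmacy. Seven days is an example; the medical team should choose the interval. Allow a home or primary care test for remote participants, keep the menopause and hysterectomy exemptions, and show the test in Table 1.

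The cost is one protocol sentence, one table entry, and one inexpensive urine test for those whose screening result is older than the interval. Remote participants would need a kit or a clinic test. No extra study visit is needed, because the investigators already send the prescription and can check the result at that step.
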